#### **2.4.8 Analysis of immunogenicity variables**

The baseline value for ADA is the original baseline from the previous studies. The value at Week 0 is the last non-missing measurement in data collected at scheduled visits: visit1, visit2, or visit1/2 in LTS11210 or EOT visit of previous studies prior to first IMP in LTS11210 study design.

ADA population will consist of all patients in the safety population with at least one post-dose evaluable ADA sample (positive, negative) in LTS11210. Patients will be analyzed according to the treatment actually received in LTS11210.

##### ***Definitions***

ADA positive patient is defined as patient with at least 1 treatment-emergent or treatment-boosted ADA positive sample during the TEAE period, where:

- Treatment-emergent ADA positive patient is defined as a patient with non-positive assay (meaning negative or missing) response at baseline but with a positive assay response during the TEAE period.
- Treatment-boosted ADA positive patient is defined as a patient with a positive ADA assay response at baseline and with at least a 4-fold increase in titer during the TEAE period.

ADA negative patient is defined as patient without a treatment-emergent or treatment-boosted ADA positive sample during the TEAE period.

##### ***ADA prevalence and titer***

The following summary will be provided based on ADA population:

- Number (%) of patients with an ADA positive sample at baseline
  - Number (%) of neutralizing antibody
  - Number (%) of non-neutralizing antibody
  - The summary statistics (including number, median, Q1, Q3, minimum and maximum) of the titer for the baseline ADA positive patients
- Number (%) of patients with an ADA negative sample at baseline

### ***ADA incidence and titer***

The following summary will be provided based on ADA population during TEAE period:

- Number (%) of ADA-negative patients
- Number (%) of ADA-positive patients
  - Number (%) of patients with neutralizing antibody
  - Number (%) of patients with non-neutralizing antibody
- Number (%) of treatment-emergent ADA-positive patients.
  - The summary statistics (including number, median, Q1, Q3, minimum, and maximum) of the peak post-baseline titer for treatment-emergent ADA-positive patients
  - Number (%) of patients with neutralizing antibody
  - Number (%) of patients with non-neutralizing antibody
- Number (%) of treatment-boosted ADA positive patients.
  - Number (%) of patients with neutralizing antibody
  - Number (%) of patients with non-neutralizing antibody

A plot of the log titers over time will be provided by treatment group. At each time point, a box plot representing the titer range, Q1, median (Q2), Q3 (excluding outliers) and outliers of the positive ADA samples will be provided. The number of ADA positive samples, the number of total subjects evaluable for immunogenicity and the proportion of ADA positive subjects at that time point will be also be provided along with the box plot.

### ***ADA and clinical safety***

The safety assessment will focus on the following events:

- Hypersensitivity (SMQ: Hypersensitivity [Narrow])
- Anaphylaxis (SMQ: Anaphylaxis [Narrow])
- Injection-site reactions (HLT: Injection site reactions)
- TEAEs leading to permanent treatment discontinuations

Number (%) of patients with these events will be summarized by ADA patient classifications (positive or negative) and previous treatment prior to enrollment into LTS11210 . The relationship between the timing and the titer of the positive ADA and events will also be explored as necessary.

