### **2.1.5 Pharmacokinetic and immunogenicity variables**

Immunogenicity (anti-sarilumab antibody) and pharmacokinetic blood samples (trough concentrations) will be collected according to the study flow chart. Pharmacokinetic samples will also be collected at or near the onset and completion of the occurrence of a serious adverse event. Note that there are some missing data after Week 48 since pharmacokinetic evaluation were added after Week 48 per Protocol Amendment 8 and by that time some patients already reach more than 48 weeks of treatment.

At each sample time the result of the ADA assay will be categorized as either positive or negative, and in the case of a positive result will be further characterized as either neutralizing or non-neutralizing.

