#### **2.4.6 Analyses of pharmacokinetic and pharmacodynamic variables**

The baseline value for PK and PD variables is the original baseline from the previous studies. The value at Week 0 is the last non-missing measurement in data collected at scheduled visits: visit1, visit2, and/or visit1/2 in LTS11210 or EOT visit of previous studies prior to first IMP in LTS11210 study design.

No PK values at baseline and Week 0 for patients with placebo treatment in EFC10832 and patients with active control (Tocilizumab) treatment in SFY13370. No ADA sample values at baseline and Week 0 for patients with active control (Tocilizumab) treatment in SFY13370.

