### ***ADA and clinical efficacy***

The following efficacy endpoints will be analyzed by ADA patient classifications (positive or negative; persistent, non-persistent; neutralizing, non-neutralizing):

- ACR20/50 response by visit
- Number (%) of patients with lack of efficacy or loss of efficacy
  - Lack of efficacy is defined as permanent treatment discontinuation due to lack of efficacy.
  - Loss of efficacy is defined as permanent treatment discontinuation due to lack of efficacy after achieving an ACR50 or EULAR Good response (at least one visit).

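### SAP 2.4.8 splits treatment-ending events by ever/never ADA positivity, a label that longer treatment makes more likely, so with no true effect ADA tends to look protective

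*SAP*

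**What the plan says.** SAP 2.4.8, Definitions, sets the label: "ADA positive patient is defined as patient with at least 1 treatment-emergent or treatment-boosted ADA positive sample during the TEAE period". Negative means no such sample in that period, which runs to 60 days after the last dose (SAP 2.1.3).

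Under ADA and clinical safety, four event types are listed, among them TEAEs that lead to permanent discontinuation. The planned output is: "Number (%) of patients with these events will be summarized by ADA patient classifications (positive or negative) and previous treatment prior to enrollment". It is followed by: "The relationship between the timing and the titer of the positive ADA and events will also be explored as necessary". Under ADA and clinical efficacy, one output by ADA class is: "Number (%) of patients with lack of efficacy or loss of efficacy". Both of those outcomes are defined as permanent discontinuation for lack of efficacy.

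Two other provisions bear on time. Under ADA incidence and titer, "the proportion of ADA positive subjects at that time point will be also be provided along with the box plot". SAP 2.4.4.1 promises events per 100 patient-years for TEAE summaries, but 2.4.8 does not repeat this. ADA baseline is the parent-study baseline, and a separate Week 0 value is defined: "The value at Week 0 is the last non-missing measurement in data collected at scheduled visits: visit1, visit2, or visit1/2 in LTS11210" or the parent study's last treatment visit.

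ADA is sampled at Week 12, every 12 weeks to Week 96, every 24 weeks after that, at EOT and at the 6-week follow-up visit (Protocol summary, Assessment Schedule; Protocol 12.1.13).

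**The concern.** The grouping variable is built from samples taken after treatment starts, and the outcome is the event that stops those samples. A patient who discontinues early has had little time to develop ADA and few samples in which to show it, so early stoppers collect in the ADA-negative column. This is immortal-time bias. The ADA-positive column is enriched for patients who stayed on treatment, and it shows a lower percentage of discontinuations even when ADA does nothing.

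Long-term safety is the primary objective, and these are the SAP's planned tables relating ADA to safety and efficacy outcomes. A ratio below 1 would read as reassurance, and a real excess would look smaller than it is. Splitting by previous treatment leaves the mechanism in place. It can also create false differences between columns, because patients with prior sarilumab may enter already positive while the others convert during LTS11210.

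**Working it through.** The plan gives no figure for this comparison, so there is none to reproduce.

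**1. Samples available.** A stop near Week 20 gives Week 12 + EOT + follow-up = 3. An end at Week 264 gives 8 (Weeks 12-96) + 6 (Weeks 120-240) + EOT in place of Week 264 (Protocol 12.1) + follow-up = 16.

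**2. Null calculation by hand.** Let a be the AE-stop hazard, o the hazard of other stops, d = a + o, λ the ADA onset hazard, p the proportion positive at entry, and T = 264 × 7/365.25 = 5.06 years. With ADA independent of stopping:

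- P(AE stop) = (a/d)(1 − e^(−dT))
- P(AE stop, never positive) = (1 − p)·a/(d+λ)·(1 − e^(−(d+λ)T))
- P(ever positive) = p + (1 − p)·λ/(d+λ)·(1 − e^(−(d+λ)T))

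Assume a = 0.06 and o = 0.07 per year, so P(AE stop) = 0.4615 × 0.4820 = 0.2225.

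*Steady onset, λ = 0.05, p = 0.* P(AE, negative) = 0.3333 × 0.5978 = 0.1993. P(positive) = 0.2778 × 0.5978 = 0.1660. ADA+: (0.2225 − 0.1993)/0.1660 = 14.0%. ADA−: 0.1993/0.8340 = 23.9%. Ratio 0.58.

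*Mostly at entry, p = 0.146, λ = 0.01.* P(AE, negative) = 0.854 × 0.4286 × 0.5075 = 0.1858. P(positive) = 0.146 + 0.854 × 0.0714 × 0.5075 = 0.1770. ADA+: (0.2225 − 0.1858)/0.1770 = 20.7%. ADA−: 0.1858/0.8230 = 22.6%. Ratio 0.92.

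**3. Ranges by simulation.** Assumed AE-stop hazards per year (year 1/later): 0.12/0.05, 0.06/0.06, 0.10/0.03. Other stops 0.07. Samples on the protocol schedule to Week 264. The anchor is Protocol 4.1.2: 19.8%, 14.6% and 4.2% treatment-emergent ADA on 150 mg q2w, 200 mg q2w and placebo.

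| ADA onset (assumed) | Crude ratio, truth 1 | Crude ratio, true hazard ratio 2 |
|---|---|---|
| Prior sarilumab: 14.6-19.8% at entry, then 1%/year (anchored) | 0.88-0.93 | 1.58-1.65 |
| First exposure: 0-4.2% at entry, 14.6-19.8% in year 1, then 1%/year (anchored) | 0.73-0.89 | 1.31-1.56 |
| 15% at entry, or conversion almost only before Week 24 | 0.90-0.97 | 1.59-1.73 |
| Steady 3-7%/year | 0.41-0.60 | 0.77-1.08 |

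For lack-of-efficacy discontinuation (assumed 2-5%/year), the null ratio is 0.86-0.99 with positives mostly at entry, 0.69-0.78 with front-loaded onset and 0.48-0.61 with steady onset.

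**4. Patient-year rates by the same label.** With hazards of 7 (AE), 3 (lack of efficacy) and 5 (other) per 100 patient-years and steady onset of 5 per 100, the null percentages are 15.8% and 26.5% (ratio 0.60), with mean treatment 4.39 and 3.39 years. Rates: 15.8/4.39 = 3.6 and 26.5/3.39 = 7.8 per 100 patient-years, ratio 0.46. That is further from 1, because the event-free time before conversion sits in the ADA-positive denominator.

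**5. What can weaken or reverse the direction.** Completers who move to commercial drug may skip the follow-up visit and its sample (Protocol 6.2). If follow-up samples add positives and 80% of completers skip them, the null ratio can reach 1.03-1.07. If lack-of-efficacy exits come late and other exits early, the lack-of-efficacy ratio is 0.92-1.19. SAP 2.1.5 also says: "Note that there are some missing data after Week 48 since pharmacokinetic evaluation were added after Week 48". It does not say whether ADA is affected. With half of the samples after Week 48 missing, the null ratio is 0.42-0.60 (steady 5%/year) or 0.85-0.90 (10% at entry plus 1%/year).

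**6. Does updating status repair it?** With ADA status updated at the first positive sample and rates compared within visit intervals, the null ratio is 0.98-1.02 and a true 2.0 gives 1.94-2.03. Splitting person-time without stratifying by time on treatment leaves a null ratio of 0.66-1.01. The EOT sample needs a rule: counting a first positive at EOT as ADA-positive at the stop moves the stratified null ratio from about 1.00 to as much as 1.12. Using only samples taken before the event gives 0.98-1.01.

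**The case against.** The case for leaving the plan alone has four parts.

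- The tables are descriptive. SAP 2.4.4 plans no systematic testing, 2.4.5 has no confirmatory efficacy analysis, and no ratio or interval by ADA status is planned. This stands: no error rate is affected, and the issue is how a reader takes the table.
- Timing is not ignored. A reader might infer that nothing planned links ADA to the time of a discontinuation. The documents do not support that, because AE discontinuation is in the event list to which the timing exploration applies. What remains is that the exploration is conditional, names no method and does not reach the lack- and loss-of-efficacy discontinuations.
- Patient-year rates are promised elsewhere. By the same ever/never label they do not remove the bias (step 4). The proportion positive at each visit is not tied to events.
- The bias may be small. Because ADA baseline is the parent-study baseline, ADA that arose in a parent study and persists counts from the first LTS11210 sample. This stands for patients with prior sarilumab.

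A reader might also infer that these tables would hide a doubling of risk. That follows only from assumed slow onset over years. In both scenarios anchored to the documents' own ADA incidences, a doubling is attenuated but still visible. Nor do the documents support saying that the table must always favour ADA, since hazard shape and skipped follow-up samples can reverse the direction.

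**Conclusion.** The point holds as a tendency of uncertain size. With no true effect, the crude split by ever/never ADA positivity tends to make ADA look protective for AE discontinuation and for lack- or loss-of-efficacy discontinuation. For AE discontinuation the anchored null ratios are about 0.88-0.93 with prior sarilumab and 0.73-0.89 with first exposure in LTS11210. Null ratios of about 0.4-0.6, with a doubling hidden, need onset spread over years at about 3-7% per year. If nearly all positives are present at entry, the bias is close to zero.

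These figures rest on assumed discontinuation hazards and ADA onset patterns, because the documents give neither for LTS11210. Protocol 4.1.2 supplies parent-study incidence, not onset timing. The consequence is misreading of a descriptive safety table, not type I error. The plan should be changed because the rule itself misleads and the remedy uses dates already collected.

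**What to change.** In SAP 2.4.8:

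- Keep the crude tables, with a footnote that ADA class depends on length of follow-up.
- For AE discontinuation and lack- or loss-of-efficacy discontinuation, replace the conditional exploration with one planned descriptive analysis. ADA status starts from Week 0 where a value exists and changes at the first positive sample. Report event rates within intervals of time on treatment, or a Cox model with time-dependent ADA.
- State that only samples taken before the discontinuation date define status at that event. First positives at EOT or follow-up do not count as ADA-positive at the event and are tabulated separately.
- As a check, add a table by ADA status at Week 24 among patients still on treatment.

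The cost is SAP text and programming, with no new visits or samples. There are limits:

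- Conversion is dated only to a 12- or 24-week interval, so a short-lived effect is diluted. A true ratio of 3 lasting 12 weeks shows as 1.00-1.15 under the pre-event rule.
- The landmark table attenuates a true 2.0 to 1.60-1.86. Taking 1283 + 7 + 168 + 454 = 1912 DMARD-combination patients (SAP 1.3), it omits about 52-102 of 340-464 AE stops. It may have only about 40 positives if conversion is slow.
- SAP 2.4.6 notes: "No ADA sample values at baseline and Week 0 for patients with active control (Tocilizumab) treatment in SFY13370". Dating status from the first LTS11210 positive is adequate for them: ignoring Week 0 altogether still gives 0.99-1.01 under the null and 1.98-2.03 for a true 2.0.

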### ***ADA and clinical efficacy***

The following efficacy endpoints will be analyzed by ADA patient classifications (positive or negative; persistent, non-persistent; neutralizing, non-neutralizing):

- ACR20/50 response by visit
- Number (%) of patients with lack of efficacy or loss of efficacy
  - Lack of efficacy is defined as permanent treatment discontinuation due to lack of efficacy.
  - Loss of efficacy is defined as permanent treatment discontinuation due to lack of efficacy after achieving an ACR50 or EULAR Good response (at least one visit).

### ***ADA and PK***

By visit descriptive summary of serum concentration of sarilumab will be provided by ADA patient classifications (positive or negative) for each actual sarilumab dose (150 mg qw, 150 mg q2w, or 200 mg q2w).

Scatter plot of serum concentration versus visit will also be provided by ADA classifications (positive or negative) and each actual sarilumab dose (150 mg qw, 150 mg q2w, or 200 mg q2w).

## **2.5 DATA HANDLING CONVENTIONS**

### **2.5.1 General conventions**

The following formulas will be used for computations of parameters.

#### ***Demographic formulas***

Age is calculated as follows:

$$Age = (informed\ consent\ date - birth\ date) / 365.25$$

BMI is calculated as follows:

$$BMI = Weight\ in\ kg / (height^2\ in\ meters)$$

#### ***Renal function formulas***

Creatinine clearance (CLcr) value will be derived using the equation of Cockcroft and Gault:

$$CLcr\ (ml/min) = (140 - age) * weight\ (kg) * (1 - 0.15 * sex\ (0-M, 1-F)) / (0.814 * creatinine\ (\mu mol/l))$$

CLcr will be calculated using weight assessed at the same visit that creatinine was assessed and age at the lab sampling date. Age is calculated as follows:

$$\text{Age} = (\text{laboratory sampling date} - \text{birth date})/365.25$$

### ***Number of TEAE per 100 patient years***

The number of TEAE per 100 patient years is defined as the total number of TEAEs divided by the total exposure (expressed under the unit of 100 patient years) of the corresponding treatment group. Specifically, it is calculated as follows for each treatment group:

$$\text{Number of TEAE/100 patient years} = (\text{Total number of TEAEs}) / \text{total treatment duration (Unit: 100 patient years)}$$

The total treatment duration is defined as [(end of TEAE period) – (date of first IMP) + 1], where the end of TEAE period is defined as minimum [(the last IMP + 60 days), (last contact date), (death date)], where the last contact date is defined as maximum [last complete AE start date, last visit date, last subject vital status date].

The number of PCSA per 100 patient years for the laboratory values, vital signs and ECGs will be defined similarly.

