
ASSESSMENT SCHEDULE
	
The last visit (EOT visit) of EFC11072, ACT11575, EFC10832, SFY13370, or EFC13752 will be used as the initial LTS11210 visit. All patients who agree to participate in the LTS11210 will need to sign a new informed consent form specific for this study. At D1, after confirmation of eligibility, patients will be enrolled in the LTS11210 study.
 
Patients will have site visits at weeks 4, 8, and 12, then every 12 weeks until the 2nd year of treatment in the study (Week 96). After 2 years of study participation, safety assessment and laboratory tests will take place at 24-week intervals. In addition, there will be visits at 24-week intervals in between regular study visits for distribution of IMP kits and recording of AEs only (in Portugal and Sweden, hematology and liver function test evaluations will be performed at all IMP dispensing visits until end of treatment). After 264 weeks in LTS11210, some assessments will no longer be required in either scheduled visits or EOT visit (see Section 1.2).
 
Additional laboratory testing (central) including hematology and liver function tests will be performed at week 2, week 6, and week 10 (site or home visits).
 
Efficacy assessments will be performed at Weeks 0, 4, 8, 12 and then every 12 weeks up to Week 96 and then every 24 weeks until the end of treatment.
 
Health economic assessments and Patient Reported outcomes (PROs) defined per initial study will be performed every 12 weeks up to Week 96 and then every 24 weeks until Week 264. PROs will not be assessed after Week 264, including EOT if EOT is after Week 264.
 
Patients who completed EFC11072 Part B will have an additional X-ray evaluation at week 48, 96, 144, 192 (<math>\pm 14</math> days for each evaluation) or at EOT if EOT prior to Week 192.
 
Electrocardiograms (ECGs) will be performed at the initial visit, week 48, 96, 144, 192, 240 and 264 or EOT. ECGs will not be performed after Week 264, including EOT if EOT is after Week 264.
 
Adverse events will be collected throughout the study.
 
Pharmacokinetic samples will be collected at V1 or V1/V2, V4 (Week 4), V7 (Week 12), every 12 weeks thereafter through year 2 and then every 24 weeks until the end of treatment and at the Post-Treatment follow-up visit 6 weeks after the end of treatment.

[figure not shown]

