- l* Clinical chemistry (fasting): fasting glucose, total proteins, calcium, sodium, potassium, Lactate Dehydrogenase, (LDH), urea nitrogen and creatinine. Creatinine clearance will be calculated during the study if clinical indicated.
- m* ANA titer will be done at screening, at Week 48, 96, 144, 192, 240, 264, 288, 336, 384, 432, 480 and EOT visit or sooner if clinical indicated (Anti-ds-DNA only if ANA titer is  $>1:160$ )
- n* Dipstick urinalysis for: specific gravity, pH, glucose, blood, ketones, proteins, bilirubin, urobilinogen, nitrite, leukocytes. If any parameter is abnormal, a urinalysis sample should be sent to central laboratory for testing. If positive for proteins, microscopic analysis will be performed by central laboratory.
- o* After Visit 7 (Week 12) between study visits the patient will have a urine pregnancy test at home on a monthly basis. Patients will be given sufficient urine pregnancy kits to take home at each successive visit for monthly testing up until the final treatment visit. When the testing coincides with a clinical visit as indicated in the flow chart, the results should be reported in the eCRF. No pregnancy test kits will be dispensed at EOT.
- p* ECG to be done at Weeks 48, 96, 144, 192, 240, 264 or EOT; No ECG will be done after Week 264 including EOT if EOT is after Week 264.
- q* Rheumatoid factor only at baseline Visit 2 (Week 0) and at Weeks 48, 96, 144, 192, 240, 264 or EOT. No Rheumatoid factor will be assessed after Week 264 including EOT if EOT is after Week 264.
- r* If throughout the study a serious adverse event (SAE) occurs in a patient, blood samples should be collected for sarilumab at or near the onset and completion of the occurrence of the event, if possible. The exact date of sample collection and last dose must be recorded on the e-CRF.
- s* Serum sample for biomarkers to be collected at screening (ie, the last treatment visit from the EFC11072 or ACT11575), Week 2, Week 12, and Week 48.
- t* Blood sample for RNA to be collected at Week 0 (baseline, prior to administration of study drug) and Week 2 (at site visit only; cancel RNA collection if home visit).
- u* Deleted.
- v* Samples for IL-6 to be collected at Screening (ie the last treatment visit from EFC11072 or ACT11575) and at V4 (Week 4), V7 (Week 12), V8 (Week 24), V9 (Week 36), and V10 (Week 48).

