Including: Prothrombin Time (PT), albumin, Alanine Aminotransferase (ALT), Aspartate Aminotransferase (AST), Alkaline Phosphatase (ALP), total bilirubin, conjugated bilirubin, unconjugated bilirubin. NOTE: after Week 264, PT will no longer be tested.
- Lipids profile (patients need to be fasting)  
Including: total cholesterol (TC), High Density Lipoprotein (HDL) cholesterol, Low Density Lipoprotein (LDL) cholesterol, triglycerides, Apolipoprotein A and Apolipoprotein B (Apolipoprotein A and B determination is not performed in SFY13370 study and results will not be available for the initial LTS11210 visit for SFY13370 patients). NOTE: after Week 264, only total cholesterol, HDL cholesterol, LDL cholesterol and triglycerides will be tested.
- Clinical Chemistry (patients need to be fasting)  
Including: fasting glucose, total protein, calcium, sodium, potassium, Lactate Dehydrogenase (LDH), urea nitrogen and creatinine. Creatinine clearance will be calculated only at initial visit and during the study if clinical indicated.
- For women of child-bearing potential: urine pregnancy testing will be performed as per study flow chart in [Section 1.2](#). From V6, the site will dispense urine pregnancy kits to the patients who will perform the test at home on a monthly basis. The pregnancy test should be completed prior to any X-ray procedure. If any interim urine pregnancy test performed by the patient is positive, the patient should immediately report to the investigator for appropriate follow-up and pregnancy reporting as appropriate.
- Urine analysis: including specific gravity, pH, glucose, blood, ketones, proteins, bilirubin, urobilinogen, nitrate, leukocytes will be performed per specifications on the study flow chart using a dipstick. If any parameter is abnormal, a urine sample should be sent to the central laboratory for testing. If positive for proteins, microscopic analysis will also be performed by central laboratory. NOTE: after Week 264, urine analysis will no longer be performed.
- ANA/Anti-ds-DNA: testing will be done per specifications on the study flow chart (see [Section 1.2](#)).
- Hepatitis B and C: serology will be determined as clinically indicated (see [Section 10.2.4](#)).
- HIV: testing will be done anytime during the study when the patient has been at risk for HIV infection as per investigator judgment.  
  

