### **12.1.13 Visit 50: Post Treatment safety follow-up visit**

Patients that discontinued prematurely before the planned end of treatment, or who completed their treatment per protocol should have this visit performed 6 weeks from end of treatment visit with the following exception:

- In patients who complete sarilumab treatment per protocol in countries where sarilumab is commercially available the post treatment follow-up visit may be cancelled if the patient initiates treatment with commercial sarilumab during the post treatment follow-up period. However, in this case, a telephone contact must be established with the patient to capture all AEs occurring up to the 1st administration of commercial sarilumab.

The Investigator will:

- Record vital signs including body temperature, blood pressure and HR and weight.
- Perform tuberculosis assessment. In case of suspicion of tuberculosis, refer the patient to a TB specialist for complete examination and additional work-up (see specific instructions in [Section 10.2.1](#)).
- Inquire regarding AE/SAEs and concomitant medications.
- Obtain urine for pregnancy test for female of child bearing potential.
- Obtain serum sample for PK (sarilumab) and for anti-sarilumab antibody.

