The duration of the treatment period in the study will be at least 264 weeks, or up to a maximum of 516 weeks (*except in the UK where the duration of treatment will be 264 weeks*) described in Protocol Amendment 9. However, some patients may complete this study with 260 week treatment duration per Protocol Amendment 8 before the approval of Protocol Amendment 9 in their countries. The total maximum duration of study participation for a patient may be up to 523 weeks.

- 1-week screening period if applicable
- 516-week maximum treatment period in LTS11210 (for the earliest patients enrolled in LTS11210 in 2010 if sarilumab is not commercialized by 2020)
- 6-week follow up period as required per protocol

Patients will either enter a 1-week screening period after the EOT visit (Visit 1 in LTS11210) in initial studies (for patients from EFC11072 Part A or Part B1 and ACT11575), or enrol directly into the treatment period (for patients from EFC11072 Part B2, EFC10832, SFY13370, or EFC13752, the EOT visit in the initial study corresponds to the randomization visit, Visit 1/2 in LTS11210).

At Visit 2 or Visit 1/2 (Week 0) after confirmation of eligibility, patients will be administered the first open-label dose of sarilumab at the investigational site and will be observed for 30 minutes for any medical events. At dosing time points occurring outside site visits, sarilumab can be injected by the patients, or by trained caregivers.

Patients will return for the safety follow-up visit 6 weeks after the EOT visit (V49). In case of early treatment discontinuation, patients are required to complete the EOT visit (V49) and to return for the 6-week safety follow-up visit (Visit 50) as well.

The study will be considered completed for a patient at the time he/she completes all the scheduled procedures.

An optional 12-week sub-study aiming to evaluate the usability of pre-filled syringe with safety system (PFS-S) will be conducted in some countries. Patients enrolled in LTS11210 at selected sites in those countries may participate in the PFS-S sub-study from Week 24 of the main study after providing written informed consent for the sub-study. However, patients may continue to participate in the main trial without participating in the PFS-S sub-study if they wish. Full details of the PFS-S sub-study are presented in [Appendix K](#).

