### ***Number of patients with special event per 100 patient-years***

The number of patients with at least one specific event per 100 patient-years will be calculated as the number of patients having a specific event in question divided by the total person-year among patients at risk of an initial occurrence of the specific event in question. In particular, it is computed as follows:

$$100 \times \frac{n}{\sum t_i}$$

Where n is the number of patients with the specific events;  $t_i$  is patient exposure time in person-year unit. For each of the specific events of interest, the exposure time for patients who have experienced the specific events will be defined as the time to first specific event in question, whereas the exposure time for those who have not had this specific event will be total duration of exposure as defined above. Please note, the time to first PCSA will be calculated using the midpoint of the time interval between the first assessment showing the PCSA and the previous assessment.

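### PCSA rates per 100 patient-years for ECG and urine pH count person-time after Week 264, when these tests are no longer scheduled

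*SAP*

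**What the plan says.** SAP 2.5.1 defines two rates.

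- **Number of events per 100 patient-years.** For adverse events, the total count is divided by total duration, from first IMP to the earliest of last IMP + 60 days, last contact and death. The paragraph ends: "The number of PCSA per 100 patient years for the laboratory values, vital signs and ECGs will be defined similarly".
- **Number of patients with an event per 100 patient-years.** A patient with the event contributes time to the first one, and for PCSAs this is placed at an interval midpoint. For the others, "the exposure time for those who have not had this specific event will be total duration of exposure as defined above".

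Neither formula has a limit tied to the last test of the parameter.

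The testing schedule is shorter than this person-time. The flow chart footnotes in Protocol 1.2 say "No ECG will be done after Week 264 including EOT if EOT is after Week 264". Protocol 10.1 says of dipstick testing "NOTE: after Week 264, urine analysis will no longer be performed". The list in Protocol 12.1.12 for an EOT visit after Week 264 contains neither test. Treatment, however, lasts at least 264 weeks or "up to a maximum of 516 weeks" (SAP 1.1). At Visit 50, six weeks after EOT, the only blood sample is for drug concentration and antibodies ("Obtain serum sample for PK (sarilumab) and for anti-sarilumab antibody", Protocol 12.1.13).

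**The concern.** The denominator suits adverse events because they are collected throughout. It does not suit a test that has stopped. After Week 264 a continuing patient adds person-time in which no scheduled ECG or urine test can find a PCSA, so the rate falls because testing ended and not because abnormalities became rarer.

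Long-term safety is the primary objective, and the error runs in the favourable direction. It also need not be equal across groups. SAP 2.3.1 presents results by previous treatment so that differences between those groups can be assessed, and groups with more follow-up past Week 264 would have their ECG rates diluted more. ECG is the main case; for urinalysis, SAP Appendix A lists only a pH criterion.

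**Working it through.** **Inputs.** Last scheduled ECG and urinalysis: Week 264 (Protocol 1.2, 10.1). Maximum treatment: 516 weeks (Protocol 6.2, SAP 1.1). End of person-time: SAP 2.5.1. Dosing every two weeks, so the last dose is taken as two weeks before EOT. The documents do not give the share of patients continuing past Week 264; that is an assumption below.

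**Plan's own figures.** Maximum participation: 1 + 516 + 6 = 523 weeks, as stated. SAP Table 6 target days: 264 × 7 + 1 = 1849 and 516 × 7 + 1 = 3613, as stated. The plan gives no PCSA rate and no bias figure to reproduce.

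**Factor.** Reported rate ÷ rate over tested time = tested person-time ÷ person-time in the SAP denominator. This assumes a constant PCSA rate and no unscheduled tests after Week 264.

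**1. One patient treated 516 weeks.**
- Last dose at Week 514 (day 3599): 3599 + 60 = 3659, but last contact at Visit 50 (Week 522) is day 3655. Factor 1849 / 3655 = 0.506.
- Last dose at Week 516 with the full 60 days: 3613 + 60 = 3673. Factor 1849 / 3673 = 0.503.

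**2. One patient treated for less time** (same method, Visit 50 as last contact).

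| Weeks treated | Last day counted | Factor |
|---|---|---|
| 264 | 1891 | 0.98 |
| 288 | 2059 | 0.90 |
| 336 | 2395 | 0.77 |
| 384 | 2731 | 0.68 |
| 432 | 3067 | 0.60 |

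**3. A treatment group.** Suppose all patients reach Week 264 and a share p continues for a mean of 126 further weeks, half of the possible 516 − 264 = 252. With 60 − 14 = 46 days after EOT, the factor is 264 / (264 + 126p + 46/7).
- p = 25%: 264 / 302.1 = 0.87
- p = 50%: 264 / 333.6 = 0.79
- p = 75%: 264 / 365.1 = 0.72

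The documents do not say that all patients reach Week 264. As a check, let those who do not continue average m weeks, let those who do average 360 weeks in total, and add 6 weeks for each patient. The factor is (264p + m(1 − p)) / (366p + (m + 6)(1 − p)).
- p = 25%: 264 / 294 = 0.90 for m = 264; 141 / 171 = 0.82 for m = 100.
- p = 50%: 264 / 318 = 0.83 for m = 264; 182 / 236 = 0.77 for m = 100.

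**4. Between groups.** If two groups have the same underlying ECG PCSA rate but 75% and 25% continue as in step 3, their reported rates stand in the ratio 0.723 / 0.874 = 0.83.

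**5. Laboratory tail.** Haematology, liver tests and chemistry continue to EOT, so only the time after EOT is untested. At 264 weeks this is 42 / 1891 = 2.2% with Visit 50 as last contact, or 46 / (264 × 7 + 46) = 2.4% with the full 60 days.

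**The case against.** Four objections carry weight.

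- **No planned table is shown to use the rate.** The laboratory, vital-sign and ECG analysis sections (SAP 2.4.4.3 to 2.4.4.5) ask for PCSA incidence, and Appendix B lists an exposure-adjusted analysis for adverse events but not for these data. This stands and limits the consequence. Even so, SAP 2.5.1 defines the rate and supplies a midpoint rule for PCSAs, so a programmer could produce it as written.
- **The main PCSA results are safe.** Percentages use patients assessed for the parameter (SAP 2.4.4). This stands. A reader might infer that all PCSA results are understated; they are not.
- **Testing after Week 264 is not zero.** Unscheduled tests count towards PCSAs (SAP 2.5.5), and the Week 264 ECG window in Table 6 has no upper limit. This also stands, and it moves the factor towards 1. But tests done for a clinical reason do not replace scheduled surveillance.
- **The laboratory tail is small.** Last contact can cut it short, and Visit 50 may be cancelled when commercial drug starts. A reader might infer a large effect from a patient who stops at 12 weeks, where 46 / (84 + 46) = 35% of person-time is untested. That describes one early discontinuer, not a group.

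It might also be argued that ECG and haematology rates are no longer comparable with each other. Their testing frequencies differ from the start and no such comparison is planned, so the point does not rest on it.

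**Conclusion.** The mismatch is real and nothing in the SAP corrects it. If PCSA rates per 100 patient-years are reported for ECG or urine pH under the rule as written, they are understated relative to the rate over tested time. On the assumptions in step 3, with all patients reaching Week 264, the group factor is about 0.87 to 0.72; the true size depends on how many continue past Week 264 and for how long. In the rate of patients with a first event, the excess time is carried by patients without a PCSA, so the effect is close to these figures when PCSAs are uncommon.

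A reader might infer that reported rates could be half the true rate. The documents do not support that for any reported figure. The factor of about 0.51 needs every patient in a group to be treated for 516 weeks. Only the earliest 2010 entrants can be; UK patients stop at Week 264 (Protocol 6.2), patients in countries where the drug is on the market stop at Week 264 or soon after marketing begins (Protocol 12.1), and some finish at 260 weeks (SAP 1.1). The laboratory tail is secondary.

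**What to change.** Decide first whether the rate is wanted. If not, delete the PCSA sentence and the PCSA midpoint rule from SAP 2.5.1, in line with Appendix B. If it is, change SAP 2.5.1 as follows.

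1. **Total number of PCSAs.** End each patient's person-time at the last assessment of that parameter, scheduled or unscheduled, within the TEAE period. Do not censor at the first PCSA here: repeat PCSAs would be counted while the time in which they arise was removed, which would inflate the rate. Alternatively, for ECG and urinalysis, restrict both the PCSAs and the person-time to the period up to the Week 264 assessment. Capping person-time alone would leave later unscheduled PCSAs in the numerator.
2. **Patients with at least one PCSA.** Use the midpoint time for patients with a PCSA, and the last assessment of that parameter within the TEAE period for patients without one.
3. **Adverse events.** Keep last IMP + 60 days, for adverse events only.

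The cost is a few sentences in the SAP and a parameter-specific censoring date in the program. The rates become slightly less favourable. No change to visits or data collection is needed.
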